11.7 Karnofsky and Lansky Performance Scores

For Karnofsky and Lansky performance scores, descriptive statistics as well as changes from baseline will be summarized and listed for each visit in Section [8.4.2](#). For each of the postbaseline assessments, change between baseline and that assessment will be calculated as follows:

Change from baseline = [post-baseline assessment date] – [baseline assessment date]

and will be summarized and presented using descriptive statistics. If the performance score is missing at either baseline or a specific postbaseline assessment for a subject, change from baseline will be missing.

The following summary will be provided:

- Summary of Karnofsky and Lansky performance scores

The following listing will be provided:

- Listing of Karnofsky and Lansky performance scores

11.8 Abdominal Ultrasound

Abdominal ultrasound assessments will be presented in the following listing and will include the date, liver size, presence of hepatomegaly, presence of ascites, and reversal of portal venous flow:

- Listing of abdominal ultrasound

12 HOSPITAL RESOURCE UTILIZATION

Hospital resource utilization will be summarized by treatment arm for the Safety Analysis Set.

The duration of hospital stay in days will be calculated as follows:

$$\text{Days in hospital} = [\text{Date of hospital discharge}] - [\text{Date of hospital admission}] + 1$$

If hospital re-admission occurs during the study, the duration of each re-admission will be calculated as noted above and the number of days in the hospital across all admissions will be summed to obtain the total duration of the hospital stay for each subject. If the date of hospital admission is prior to the date of informed consent, the informed consent date will be used as the date of admission. If the subject is still in the hospital at the time of study completion, death, or early termination, the discharge date will be recorded as “Not Applicable” on the eCRF and the date of study completion/early termination/death will be used as the discharge date. The total duration of the hospital stay will be summarized. The number of subjects who were hospitalized prior to informed consent and the number who were still hospitalized at the end of study participation will be tabulated.

The total number of days in Intensive Care Unit (ICU) will be calculated using the same method noted above and summarized.

Inpatient resource use and/or use of diagnostic tests during the initial hospital stay or during any re-admissions will be summarized and listed including the following:

- Number of blood transfusions

- Total number of units for all transfusions received
- Total number of days of ventilator use
- Type of dialysis
- Total number of days on dialysis
- Number of liver biopsies
- Number of bone marrow biopsies
- Number of other biopsies

The following summary will be provided:

- Summary of hospital stay and resource utilization

The following listings will be provided:

- Listing of hospital and ICU stay
- Listing of inpatient resource utilization

13 HEALTH-RELATED QUALITY OF LIFE

Health-related quality of life results will be summarized by treatment arm for the Safety Analysis Set.

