### 2.2 Secondary Objectives

The key secondary objective of the study is to compare the efficacy of defibrotide prophylaxis in addition to BSC (DP arm) vs BSC alone (BSC arm) for the prevention of VOD as measured by VOD-free survival by Day +100 post-HSCT in patients who are at high risk or very high risk for developing VOD.

Other secondary objectives of the study are as follows:

- To further compare the efficacy of defibrotide prophylaxis in addition to BSC (DP arm) vs BSC alone (BSC arm) on additional variables, as follows:
  - Incidence of VOD by Day +30 post-HSCT
  - VOD-free survival by Day +180 post-HSCT
  - Non-relapse mortality (NRM) by Day +100 and by Day +180 post-HSCT
  - Incidence of VOD-associated multi-organ dysfunction (MOD) (i.e., severe VOD) by Day +30 and by Day +100 post-HSCT (in those patients who develop VOD)
  - Proportion of patients who have resolution of VOD by Day +180 post-HSCT and time to resolution of VOD (in those patients who develop VOD)
  - Incidence of VOD after Day +30 post-HSCT, by Day +100, and by Day +180 post-HSCT
- To compare the health-related quality of life using the following questionnaires:
  - 5-Level EuroQol-5D (EQ-5D-5L) (adults only)
  - EuroQol-5D for Youth (EQ-5D-Y), proxy version 1 (pediatric patients 4 to 7 years of age)
  - EQ-5D-Y, self-report version 1 (pediatric patients 8 to <16 years of age)
- To characterize the pharmacokinetics of defibrotide
- To compare the overall safety of defibrotide in addition to BSC vs BSC alone, including AE profile, SAE profile, laboratory abnormalities, and vital signs (including peri-infusional vital signs for patients who receive defibrotide)
- To compare the overall safety of defibrotide in addition to BSC vs BSC alone by comparing the incidence of grades 2, 3, and 4 acute GvHD by Day +30, Day +100, and Day +180 post-HSCT, and the incidence of chronic GvHD at Day +180 post-HSCT
- To compare graft failure and time to neutrophil and platelet engraftment

Defibrotide (JZP-381)  
Clinical Trial Protocol: 15-007 Version 4.0

Jazz Pharmaceuticals, Inc.  
20 August 2018

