4.3.2.3 Other Secondary Endpoints

Other secondary efficacy endpoints will be tested without multiplicity adjustments, and nominal p-values will be reported. Other secondary efficacy endpoints include the following:

- Incidence of VOD by Day +30 post-HSCT
- VOD-free survival by Day +180 post-HSCT
- NRM by Days +100 and +180 post-HSCT

- Incidence of VOD-associated MOD (ie, severe VOD) by Days +30 and +100 post-HSCT (in those subjects who develop VOD)
- Proportion of subjects who have resolution of VOD by Day +180 post-HSCT and time to resolution of VOD
- Incidence of VOD after Day +30 post-HSCT up to Days +100 and +180 post-HSCT
- Health-related quality of life using EQ-5D-5L (adults only), EQ-5D-Y (proxy version 1; pediatric subjects 4 to 7 years of age), and EQ-5D-Y (self-report version 1; pediatric subjects 8 to <16 years of age)
- Pharmacokinetics of defibrotide
- Safety of defibrotide in addition to BSC vs BSC alone, including AE profile, SAE profile, laboratory abnormalities, and vital signs
- Incidence of Grades 2, 3, and 4 acute GvHD by Days +30, +100, and +180 post-HSCT, and the incidence of chronic GvHD by Day +180 post-HSCT
- Graft failure and time to neutrophil and platelet engraftment

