6.2 Intent-to-Treat Analysis Set (ITT)

The ITT Analysis Set will include all randomized subjects. This will be the primary analysis set for the primary efficacy endpoint and all other efficacy endpoints. Subjects will be analyzed by the treatment they were randomized to receive.

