6.4 Safety Analysis Set

The overall safety population will include all subjects randomized to the DP arm who receive at least 1 dose of defibrotide and all subjects randomized to the BSC arm. Subjects will be analyzed by the treatment they actually receive.

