10.2.2 Other Secondary Efficacy Endpoints

These other secondary efficacy endpoints will be tested without multiplicity adjustments, and nominal p-values will be reported. The ITT Analysis Set will be used for these analyses.

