13.1.2 EQ VAS Score

The EQ VAS score at baseline and each of the post-HSCT assessments will be summarized and presented using descriptive statistics. A higher EQ VAS score represents better QoL. For each of the post-HSCT assessments, change between baseline and that assessment in the EQ VAS score will be calculated and will be summarized and presented using descriptive statistics.

$$\text{Change in the EQ VAS} = [\text{EQ VAS at the post-HSCT assessment}] - [\text{EQ VAS at baseline}]$$

The following summary will be provided:

- Summary of EQ-5D-5L VAS score for adult subjects (age ≥ 16 years)

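### The SAP lists quality of life among endpoints to be tested and sets ITT for efficacy, but Section 13 plans only descriptive tables in the Safety Analysis Set, with no between-arm estimate

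*SAP*

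**What the plan says.** The objective is comparative. Protocol 2.2 reads "To compare the health-related quality of life using the following questionnaires", and the SAP repeats it in 4.2.2.

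The front of the SAP treats HRQoL as a tested endpoint. Section 4.3.2.3 opens with "Other secondary efficacy endpoints will be tested without multiplicity adjustments, and nominal p-values will be reported", and its list includes "Health-related quality of life using EQ-5D-5L (adults only), EQ-5D-Y (proxy version 1; pediatric subjects 4 to 7 years of age", with the self-report EQ-5D-Y alongside. Section 7.2 repeats the testing rule and applies it to other endpoints in general, secondary efficacy endpoints included.

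On the analysis set, SAP 6.2 says of ITT: "This will be the primary analysis set for the primary efficacy endpoint and all other efficacy endpoints". Section 10.2.2 restates this for other secondary efficacy endpoints: "The ITT Analysis Set will be used for these analyses".

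The section that will be programmed says something else: "Health-related quality of life results will be summarized by treatment arm for the Safety Analysis Set" (SAP 13). SAP 6.4 defines that set as "all subjects randomized to the DP arm who receive at least 1 dose of defibrotide and all subjects randomized to the BSC arm", grouped by treatment actually received. For EQ VAS, SAP 13.1.2 plans that "change between baseline and that assessment in the EQ VAS score will be calculated and will be summarized and presented using descriptive statistics". For the five dimensions, 13.1.1 classes each patient as improved, unchanged, deteriorated or unknown relative to baseline. Sections 13.2 and 13.3 repeat the scheme for the two youth versions.

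**The concern.** A programmer cannot satisfy 4.3.2.3, 7.2 and 6.2 together with Section 13. One route calls for a nominal test by randomised arm in ITT. The other has no test, and its population is defined by a different rule in each arm. SAP 5, which records departures from the planned analyses, does not mention the difference.

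At stake is whether the secondary objective gets an answer. EQ-5D forms are scheduled at baseline and at seven later occasions (protocol Appendix 1: Days +7 and +15, discharge, Days +30, +60, +100 and +180). With no specified contrast, readers will subtract one arm's mean change from the other's, without an interval and in groups that are not strictly the randomised ones.

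**Working it through.** The documents give no sample size, effect size, SD or correlation for HRQoL, so there is no HRQoL figure to reproduce. The check is mainly of consistency.

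**1. The sections side by side**

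| Question | SAP 4.3.2.3, 7.2, 6.2 | SAP 13 with 6.4 |
|---|---|---|
| Tested? | Yes, nominal p-values | No test described |
| Set | ITT (all randomised) | DP: at least one dose; BSC: all randomised |
| Grouping | As randomised | As treated per 6.4; by treatment arm per 13 |
| Between-arm estimate or CI | Implied by testing | None |
| Role of baseline | Not stated | Change score and change category, not a covariate |

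**2. Size of the set difference (assumed inputs)**

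The fraction u of DP patients never dosed is not given. With 200 planned per arm (SAP 4.6) and u of 1%, 2% or 5%:

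- DP patients lost from the Safety set: 200 × 0.01 = 2, 200 × 0.02 = 4, 200 × 0.05 = 10.
- BSC patients lost: 0.

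If undosed patients differ from dosed ones by D standard deviations, the DP mean shifts by u × D. For D of 0.5 to 1 this runs from 0.01 × 0.5 = 0.005 SD to 0.05 × 1 = 0.05 SD. Even that requires the undosed patients to have completed post-baseline forms.

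**3. Precision from using baseline as a covariate (assumed inputs)**

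Let ρ be the correlation between baseline and follow-up EQ VAS, with equal SD at both times. Up to a common factor, the variance of the between-arm difference is:

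- follow-up means only: 1
- change scores: 2(1 − ρ)
- baseline-adjusted: 1 − ρ²

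The ratio of adjusted to change score is (1 − ρ²) / [2(1 − ρ)] = (1 + ρ)/2.

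| ρ (assumed) | Change score | Adjusted | Ratio | Equivalent gain in patients |
|---|---|---|---|---|
| 0.3 | 1.40 | 0.91 | 0.65 | 1/0.65 = 1.54, or 54% |
| 0.5 | 1.00 | 0.75 | 0.75 | 1/0.75 = 1.33, or 33% |
| 0.7 | 0.60 | 0.51 | 0.85 | 1/0.85 = 1.18, or 18% |

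The change score is less precise than plain follow-up means only while 2(1 − ρ) > 1, that is for ρ below 0.5. The two tie at 0.5 and the change score is better above it. The adjusted estimate has the smallest variance at all three values.

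**4. Which covariates make sense**

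The age stratum splits at >16 versus ≤16 years (SAP 4.5). Both EQ-5D-Y versions are for patients under 16, so the stratum is constant in those models. EQ-5D-5L starts at 16 (SAP 13.1.1), so only 16-year-olds fall in the lower stratum. Risk stratum is the usable one. Protocol Table 5 has no instrument below age 4, so any HRQoL analysis covers only part of ITT.

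**The case against.** The strongest reply is that this is loose drafting. The list in SAP 4.3.2.3 mirrors the secondary objectives and also holds pharmacokinetics, adverse events, laboratory data and engraftment, which cannot all be ITT efficacy tests. SAP 10.2.2, where the tests are actually specified, has six subsections and none is HRQoL. Protocol 9.8.3 lists its tested secondary efficacy endpoints without HRQoL. Protocol 9.9 plans only descriptive HRQoL summaries and repeats the comparative objective directly beneath, so the protocol seems content to meet it descriptively. The objective of comparing safety is handled with tables in the same way.

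Much of this stands. The absence of an estimator begins in the protocol; what the SAP adds is the testing statement and the Safety set. The reply does not remove the conflict, because SAP 7.2 states the testing rule again in general terms, and nothing explains why patient-reported outcomes move to a safety population.

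Three stronger readings are tempting and should be resisted:

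- *That the SAP states outright that HRQoL will be tested in ITT.* No single sentence does. It follows only by joining 4.3.2.3 with 6.2.
- *That the baseline questionnaire goes unused.* It defines every change category and the EQ VAS change. It is only not used as a covariate.
- *That rescue defibrotide moves BSC patients into the DP column.* SAP 8.3 groups safety summaries by treatment received during the Prophylaxis Phase, and Section 13 says by arm.

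**Conclusion.** The inconsistency is real, and the comparative objective has no specified between-arm estimate. It is a minor point: HRQoL lies outside the controlled testing sequence and cannot affect the primary or key secondary conclusion.

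The analysis-set asymmetry is a matter of principle more than of size. The documents give no undosed fraction, and under the assumed 1% to 5% the shift is at most 0.05 SD. The precision gain is a variance ratio of 0.65 to 0.85 against a change-score difference. It rests on an assumed correlation of 0.3 to 0.7 and equal SDs, and the comparator is what a reader would compute from the tables, not an analysis that the SAP plans. It would be too strong to call the change-score difference the least precise option, since that fails against follow-up means once the correlation reaches 0.5.

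**What to change.** Before database freeze, reconcile SAP 4.3.2.3, 6.2, 7.2 and 13:

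- Analyse HRQoL by randomised arm in ITT subjects eligible for each instrument, stating that none covers children under 4.
- For EQ VAS, report per instrument the between-arm difference with 95% CI from a linear model adjusting for baseline VAS and risk stratum. Leave out the age stratum for the reason in step 4 of the working.
- Name in advance the visit or visits to be modelled, and give EQ-5D visit windows, which SAP 8.4 lacks. Testing all seven occasions for three instruments would produce 7 × 3 = 21 nominal p-values.
- Label p-values as nominal and conditional on survival and form completion.
- Keep the descriptive tables, and record the change in SAP 5.

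The cost is SAP wording and one standard model. The downside is that the estimates describe surviving patients who completed the form, which is why the label is needed. If the sponsor prefers to stay with protocol 9.9, the minimum is to state in 4.3.2.3 and 7.2 that HRQoL is descriptive only and to justify the chosen set. That removes the contradiction but leaves the objective without an estimate.

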13.1 EQ-5D-5L

13.1.1 EQ-5D-5L Dimension

For each of the 5 dimensions of mobility, self-care, activity, pain, and anxiety based on the descriptive system of the EQ-5D-5L, the numbers and percentages of subjects for all categories (the five levels of reported problems and question not completed) at baseline and each of the post-HSCT assessments will be presented. For each of the post-HSCT assessments, change between baseline and that assessment in each dimension will be categorized as follows for a specific subject:

- Condition improved, if the reported level of problem is lower at that assessment than at baseline
- Condition unchanged, if the reported level of problem remains the same
- Condition deteriorated, if the reported level of problem is higher at that assessment than at baseline
- Unknown, if the reported level of problem is missing either at baseline or at that assessment

The numbers and percentages of subjects for all the above-mentioned categories will be presented for each dimension at each of the post-HSCT assessments.

The following summaries will be provided:

- Summary of EQ-5D-5L dimensions for adult subjects (age ≥ 16 years) by assessment
- Summary of change in EQ-5D-5L dimensions from baseline for adult subjects (age ≥ 16 years) by assessment

The following listing will be provided including results for each of the 5 dimensions and the visual analogue scale (VAS) score:

- Listing of EQ-5D-5L

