## 1.5 Justification for Selection of the Patient Population

In an unselected population, the incidence of VOD following HSCT has been estimated to be approximately 10% to 15% ([Coppell et al. 2010](#)). The incidence of VOD is estimated to be 20% to 25% in patients at high risk of VOD and 30% to 60% in patients at very high risk of VOD ([Table 3](#)). The assumed VOD-free survival at Day +30 post-HSCT considered in the design of this study takes into account a split between high risk and very high risk patients of 65% and 35%, respectively, which will be ensured at interim analyses, at the end of the study, and monitored throughout.

The all-cause mortality at this early time point (i.e., Day +30 post-HSCT) is not high; however, deaths do occur secondary to infection, GvHD, cardiopulmonary causes, relapse of underlying malignancy, and liver disease (primarily VOD). A recent publication noted a

Defibrotide (JZP-381)  
Clinical Trial Protocol: 15-007 Version 4.0

Jazz Pharmaceuticals, Inc.  
20 August 2018

decrease in all-cause mortality throughout the post-transplant course following myeloablative allogeneic HSCT; although Day +30 post-HSCT mortality was not separately reported, it would be estimated to be between 5% to 10% by Day +30 post-HSCT (Gooley et al. 2010). A separate study of intravenous versus oral busulfan for myeloablative HSCT reported 4% and 8% all-cause mortality by Day +30 post, respectively (Gupta et al. 2005). Given this, the incidence rate of VOD or death by Day +30 post-HSCT for this study (although it cannot be separately estimated by risk factor for VOD) would likely be 25% to 30% in patients at high risk of developing VOD and 33% to 63% in patients at very high risk of developing VOD.

The majority of patients in the high-risk population is predicted to be adult, whereas, patients in the very high-risk population are expected to be pediatric due to the presence of inherited diseases such as osteopetrosis and inherited hemophagocytic syndromes. There will however be adults in the very high-risk population (those receiving the ozogamicin antibody conjugates) and pediatric patients in the high-risk population (those with pre-existing liver disease and neuroblastoma).

**Table 3 Estimated Risk of Developing Veno-Occlusive Disease by Day +30 Following Hematopoietic Stem Cell Transplant in High-Risk and Very High-Risk Patient Populations**

Patient Subset	Characteristics	Estimated Incidence of VOD by Day +30 post-HSCT	Reference

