**Table 9 Karnofsky and Lansky Performance Scores**

Percentage	Karnofsky Scale (Patients ≥16 years of age)	Lansky Scale (Patients <16 years of age)
100%	Normal, no complaints, no evidence of disease	Fully active
90%	Able to carry on normal activity, minor signs or symptoms of disease	Minor restriction in physically strenuous play
80%	Normal activity with effort, some signs or symptoms of disease	Restricted in strenuous play, tires more easily, otherwise active
70%	Cares for self, unable to carry on normal activity or to do active work	Both greater restriction of and less time spent in active play
60%	Requires occasional assistance from others but able to care for most needs	Ambulatory up to 50% of time, limited active play with assistance/supervision
50%	Requires considerable assistance from others and frequent medical care	Considerable assistance required for any active play, fully able to engage in quiet play
40%	Disabled, requires special care and assistance	Able to initiate quiet activities
30%	Severely disabled, hospitalization indicated, death not imminent	Needs considerable assistance in quiet activities
20%	Very sick, hospitalization necessary, active support, treatment necessary	Limited to very passive activity initiated by others
10%	Moribund, fatal process progressing rapidly	Completely disabled, not even passive play

Source: [Karnofsky et al. 1948](#); [Lansky et al. 1987](#).

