7 GENERAL CONSIDERATIONS

7.1 General Methods

The statistical principles applied in the design and planned analyses of this study are consistent with ICH E9 guidelines (ICH 1998).

Analysis datasets will be created according to Clinical Data Interchange Standards Consortium (CDISC) standards. SAS® version 9.3 (or higher) will be used to perform all data analyses and to generate tables, figures, and listings.

Summaries will order the treatment display from left to right as follows: DP (study treatment), BSC (control), and Total if a total column if applicable. Listings will include the randomized treatment arm, unique subject number, age, gender, and race. They will be sorted by treatment arm and then by subject number within treatment arm.

Unless otherwise specified, continuous data will be summarized using descriptive statistics comprising the number of subjects with data to be summarized (n), mean, standard deviation (SD), median, minimum (min) and maximum (max). Categorical variables will be presented using counts and percentages. Every category will be kept in the summary even if it has 0 subjects. Summary statistics of central tendency will be reported to one more decimal place than the collected data. Summary statistics of variability will be reported to one more decimal place than the commensurate measure of central tendency. For example, the mean and median for age will be reported to one decimal place because it is collected in full years. The standard deviation

of age will then be reported to 2 decimal places. P-values > 0.9999 will be presented as ' >0.9999 ' and p-value < 0.0001 will be presented as ' < 0.0001 '.

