8 DATA HANDLING CONVENTIONS

8.1 Missing Data

8.1.1 Imputation of Non-Date Missing Data

Missing data occurs when any requested data is not provided, leading to blank fields on the collection instrument. These data will be indicated by the use of a "blank" in subject listing displays. Note that if any missing data is imputed, the imputed data will only be used in

summaries, and will not be included in any listing. Answers such as “Not applicable” and “Not evaluable” are not considered to be missing data and should not be displayed as missing.

Subjects with the designation of treatment relationship for AEs and SAEs missing will have the worst case assumed to impute the relationship: if relationship to study treatment is missing it will be assumed to be “Yes”. There will be no other imputation for missing data other than as described in Section [8.1.2](#) for partial dates and times.

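### The EQ-5D change tables place patients who have died in 'Unknown' with missed forms, and the EQ VAS and performance-score summaries show no deaths beside n

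*SAP*

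**What the plan says.** SAP 13.1.1 sorts each adult's change in each EQ-5D-5L dimension into improved, unchanged, deteriorated, or "Unknown, if the reported level of problem is missing either at baseline or at that assessment". All four are displayed: "The numbers and percentages of subjects for all the above-mentioned categories will be presented for each dimension at each of the post-HSCT assessments". The denominator of those percentages is not given. SAP 13.2.1 (EQ-5D-Y self-report) and 13.3.1 (proxy version) apply the same scheme.

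For the visual analogue scale, SAP 13.1.2 says only that "The EQ VAS score at baseline and each of the post-HSCT assessments will be summarized and presented using descriptive statistics", and 13.2.2 and 13.3.2 follow it. Under SAP 7.1, continuous summaries are made in subjects with data, with n shown. For Karnofsky and Lansky scores, SAP 11.7 says: "If the performance score is missing at either baseline or a specific postbaseline assessment for a subject, change from baseline will be missing". SAP 8.1.1 closes off any other handling: "There will be no other imputation for missing data other than as described in Section" 8.1.2, which concerns partial dates.

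None of these sections mentions death. SAP 13 uses the Safety Analysis Set by treatment arm. Comparing health-related quality of life is a secondary objective in Protocol 2.2 and SAP 4.2.2.

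**The concern.** Death is a known outcome, and the worst one. Labelling it 'Unknown' mixes it with ordinary non-response, which has a different meaning and a different cause. In the VAS and performance-score summaries the patient simply leaves n, and nothing beside n says why.

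This does little harm if deaths are few or equal in the two arms. The trial, however, tests a treatment meant to prevent a condition that Protocol 3.2 describes as often fatal once organ dysfunction is present, and EQ-5D is collected to Day +180. Deaths may therefore differ by arm. If they do, the arms are compared in patients selected by survival, and these tables do not let the reader see how much of a difference comes from that.

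**Working it through.** The plan states no figure for this point, so there is nothing to reproduce. The check applies the written rules and then illustrates their effect.

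**Where a patient who has died goes**
- EQ-5D change tables: the level at that visit is missing, so the patient is 'Unknown'.
- EQ-5D level tables: either 'question not completed' or absent altogether. The SAP does not say which.
- EQ VAS and Karnofsky/Lansky: no score, so the patient is outside n and outside the mean.

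**How many patients**

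Of all-cause mortality, Protocol 1.5 says "it would be estimated to be between 5% to 10% by Day +30 post-HSCT". With 200 per arm that is 0.05 × 200 = 10 to 0.10 × 200 = 20 per arm by Day +30, over all ages. Each questionnaire covers one age band (16 years and over, 8 to under 16, 4 to 7) and patients under 4 have none, so every EQ-5D table has fewer than 200 per arm. No mortality is given for Day +100 or Day +180.

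**Effect on the 'deteriorated' row**

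Let d be the proportion dead and q the proportion of survivors who deteriorated, equal in both arms. Assume no missed forms. With all subjects in the denominator, the row shows q(1 − d). Take q = 0.30, d = 0.20 in arm A and d = 0.10 in arm B (both assumed).

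| Presentation | Arm A | Arm B |
|---|---|---|
| 'Deteriorated', all subjects in denominator | 0.30 × 0.80 = 24% | 0.30 × 0.90 = 27% |
| 'Deteriorated', 'Unknown' left out of denominator | 30% | 30% |
| Deteriorated or died | 24% + 20% = 44% | 27% + 10% = 37% |

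The gap in the first line is q(dA − dB):
- deaths 5 points apart: 0.30 × 5 = 1.5 points, or 0.50 × 5 = 2.5 points if q = 0.50;
- deaths 10 points apart: 3.0 or 5.0 points;
- deaths equal: 0.

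The 'improved' and 'unchanged' rows shrink by the same factor, so the distortion is not in one direction across the table.

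**Whether the 'Unknown' row reveals it**

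Let m be the share of living patients who miss the form. Then 'Unknown' = d + (1 − d)m. Arm A with d = 0.20 and m = 0 shows 20%. Arm B with d = 0.10 shows 20% when 0.10 + 0.90m = 0.20, that is m = 1/9 (11%). If missing is unrelated to change, 'deteriorated' in arm B becomes 0.30 × 0.90 × 8/9 = 24%. The two arms then have identical tables although one has twice the deaths.

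**The case against.** The case on the other side has weight, and most of it stands as a limit on the point.

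- **Deaths are not lost from the trial.** Death is an event in the primary and key secondary endpoints and in VOD-free survival by Day +180. It also appears in non-relapse mortality and in adverse events leading to death. A reader might infer that a survival harm is hidden, but the documents do not support that. The gap is confined to these tables.
- **'Unknown' is a displayed row.** A reader might infer that all these summaries cover survivors only. That is exact for the VAS and performance scores. In the EQ-5D change tables the patients remain visible but pooled, and the effect on percentages depends on an unstated denominator. Table shells sit in a separate document (SAP 3) and might fix the denominator. The four categories, however, are set in the SAP itself.
- **The summaries are descriptive.** Protocol 9.9 plans descriptive statistics, and SAP 13 and 11.7 name no test, although SAP 4.3.2.3 announces nominal p-values for a list that includes quality of life. Karnofsky/Lansky is a safety assessment (Protocol 6.8), so the secondary objective does not cover it.
- **Later mortality is unknown.** A reader might infer at least 10% dead by Day +100. The Day +30 range supports only at least 5%.
- **Scoring death as 0 is not the remedy.** It mixes survival with quality of life, and the performance scales end at 10%, "Moribund, fatal process progressing rapidly", so 0 is not a defined score.

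What does not stand is the suggestion that mortality tables elsewhere are enough. They do not say which patients in the 'Unknown' row of a given questionnaire, age band and visit had died.

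**Conclusion.** The point holds as a minor gap in the SAP. By default, death is pooled with non-response in the EQ-5D change tables and leaves the VAS and performance-score summaries without a count. The primary result and type I error are unaffected.

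The size depends on how far deaths differ by arm. Under the assumptions shown, a difference of 5 to 10 percentage points in deaths shifts the 'deteriorated' row by 1.5 to 5.0 points in favour of the arm with more deaths, if all subjects are in the denominator. There is no shift if deaths are equal. Death rates after Day +30, the share of survivors deteriorating and the denominator are all assumptions. The pooling itself follows directly from the written rule.

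**What to change.** - **SAP 13.1.1, 13.2.1 and 13.3.1:** add a 'Died' category at each visit and keep 'Unknown' for missing data in living patients. Set the denominator to all Safety Analysis Set subjects in that age band. In the illustration the table would still read 24% v 27% deteriorated, but with 20% v 10% died beside it, so the reader sees both.
- **SAP 13.1.2, 13.2.2, 13.3.2 and 11.7:** show the cumulative number dead by arm and visit beside n, and label the means and changes as 'while alive'. Do not add a summary that scores death as 0.
- **While editing SAP 11.7:** its change formula subtracts assessment dates instead of scores and should be corrected.

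The cost is one extra row and one extra column. Protocol Appendix 1 already collects survival status at baseline and throughout follow-up to Day +180, so no new data are needed.
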